6.0 Study-Wide Number of Subjects*

- We anticipate an overall study sample of 54 participants.

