8.22 Participant intervention acceptability (Aim one): The Patient Experience Questionnaire (PEQ), developed by the investigator, will be used to summarize overall patient-reported acceptability in this study. Summary measures of median/range and mean/SD for total categorical PEQ scores, the time in weeks from the initial to follow-up intervention visit, and the number of completed intervention sessions will be reported.

8.23 Participant pain barriers (Aim two): Attitudinal barriers to pain management will be measured using the BQ-II which measures four attitudinal realms with 27 self-rated questions about pain beliefs. The BQ-II has been used in cancer pain studies with psychometrics demonstrating validity and reliability. For cancer patients, internal consistency of 0.89 (mean 1.52, SD 0.73) was reported and higher barriers were significantly correlated with increased age ($r=0.18$, $P=0.02$).³⁰ The total score for the BQ-II and PSEQ will be calculated at study entry and after the first follow-up visit and scores will be summarized (median/range, mean/SD). The paired difference in PSEQ and BQII will be estimated along with a 90% confidence interval. If additional sessions are completed, the scores for PSEQ and BQII will be plotted over time and trends will be explored with graphical methods. Spearman's correlation between the PSEQ and BQII will be estimated along with a 90% confidence interval at each measured time point.

8.24 Participant self-efficacy (Aim two): The study team will look at the correlation among the measures being explored, described herein: Pain self-efficacy will be measured using the PSEQ. In patients with a history of chronic pain and mean pain level rated at 6.2 out of 10, PSEQ demonstrated excellent internal consistency with an alpha of 0.92 and a test-retest reliability from baseline to three months of $r=0.73$, $P<0.001$.³¹ The total score for the BQ-II and PSEQ will be calculated at study entry and after the first follow-up visit and scores will be summarized (median/range, mean/SD). The paired difference in PSEQ and BQII will be estimated along with a 90% confidence interval. If additional sessions are completed, the scores for PSEQ and BQII will be plotted over time and trends will be explored with graphical methods. Spearman's correlation between the PSEQ and BQII will be estimated along with a 90% confidence interval at each measured time point.

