8.25 Participant engagement in goal-setting (Aim two): Observed Engagement will be evaluated using the instrument developed by the investigator for this study in which behaviors indicative of active goal setting will be tabulated by the PI or RA. Observed engagement will be summarized categorically, and salient quotes will be extracted into the OET to give voice to participant experiences in study results dissemination.

8.25.1 The study team will look at the correlation among the measures being explored, specifically, pain barriers (BQII) and self-efficacy (PSEQ). The paired difference in BQII and PSEQ scores from sessions one and four will be estimated, along with a 90% confidence interval. If additional sessions are completed, the scores for BQII and PSEQ will be plotted over time and trends will be explored with graphical methods. Spearman's correlation between BQII and PSEQ will be estimated along with a 90% confidence interval at each measured time point.

8.26 MI intervention fidelity: Fidelity to MI methods will be assessed on 33% of interviews using the MISHCE which was developed specifically to measure fidelity in brief healthcare encounters. MISHCE evaluates the degree to which the person providing the MI session follows five domains key to MI. The domains are: 1) MI philosophy, 2) health interviewing, 3) motivation, 4) MI principles, and 5) interpersonal process. Each domain has specific behaviors that are rated as 1) deficient, 2) developing, 3) accomplished, or 4) N/A. MISHCE demonstrated acceptable internal consistency (0.75, CI 95%), good inter-rater reliability (15 of 22 intraclass correlation coefficients were excellent, 5 were good, 1 was fair and 1 was poor), and good-to-excellent test-retest reliability.³² Fidelity assessment will be conducted by the PI or RA.

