9.0 Procedures Involved*

Testing Feasibility of Motivational Interviewing for Patient-Reported Cancer Pain Goals

9.1 Study design:

This is a single-arm pilot study to assess feasibility and acceptability of a motivational interviewing intervention which will entail two-to-four intervention sessions per participant, participant completion of a battery of questionnaires specific to the intervention session, an investigator-led MI intervention at each session, and summary statistics (described below).

9.2 Study Procedures:

After written informed consent has been obtained and verbal consent confirmed participation in this study will involve between two and four intervention sessions.

9.21 Study Participation Compensation: Participants will be compensated with \$25 gift cards at the first and last visits (anticipated to be visits 1 and 4). Pending receipt of additional funding for participant compensation, participants may also be compensated at visits 2 and 3, if these are in addition to the first and last visits, and if this funding is granted to the research study.

9.22 Intervention Sessions: Each intervention session will include a battery of questionnaires, an MI intervention, and the investigator completing a goal(s) summary for the participant to take away. Participants may opt to complete Intervention Sessions 2, 3, and 4 in person on the DFCI campus or via telephone (or a mix). Session-specific content is outlined below. Session-specific content outlined below.

Testing Feasibility of Motivational Interviewing for Patient-Reported Cancer Pain Goals

Session 1:

Questionnaires:	Demographics survey* Pain location diagram (paper and pencil) BQ-II* PSEQ*
MI Intervention	Investigator-led discussion (described below)
Goals Summary	Completed by investigator
Gift Card (\$25)	Disbursed

* Paper and pencil form or tablet computer per participant preference.

Sessions 2 & 3:

Questionnaires:	BQ-II* PSEQ*
MI Intervention	Investigator-led discussion (described below)
Goals Summary	Completed by investigator
Gift Card (\$25)	None (Pending additional funding)

* Paper and pencil form or tablet computer per participant preference.

Session 4:

Questionnaires:	BQ-II* PSEQ* PEQ*
MI Intervention	Investigator-led discussion (described below)
Goals Summary	Completed by investigator
Gift Card (\$25)	Disbursed

* Paper and pencil form or tablet computer per participant preference.

Testing Feasibility of Motivational Interviewing for Patient-Reported Cancer Pain Goals

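### The session one-to-four change in BQ-II and PSEQ leaves out every score from participants who stop before session 4; a mixed model would use them at little cost

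*Combined protocol and SAP*

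**What the plan says.** Section 9.22 lists BQ-II and PSEQ among the questionnaires at sessions 1, 2, 3 and 4. Attendance will vary: "participation in this study will involve between two and four intervention sessions", and section 7.1 ties the number to clinic schedules and the close of data collection. Section 6.0 states: "We anticipate an overall study sample of 54 participants".

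Change is defined in two ways.

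- Sections 8.23 and 8.24: total scores "will be calculated at study entry and after the first follow-up visit and scores will be summarized". The next sentence reads: "The paired difference in PSEQ and BQII will be estimated along with a 90% confidence interval". In context this is entry versus first follow-up, normally session 2 minus session 1.
- Section 8.25.1: "The paired difference in BQII and PSEQ scores from sessions one and four will be estimated, along with a 90% confidence interval".

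The remaining scores have two uses. One is graphical: "If additional sessions are completed, the scores for BQII and PSEQ will be plotted over time and trends will be explored with graphical methods". The other is Spearman's correlation between the two scales, which "will be estimated along with a 90% confidence interval at each measured time point". Section 8.2 contains no repeated-measures model, and section 11.1 refers back to it for the analysis.

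**The concern.** A simple pair needs both of its ends. Someone who attends two or three sessions supplies a baseline and one or two later scores, and none of them enters the one-to-four difference. Participation may end after two sessions, and section 8.21 sets a target of only 60% for completing even one follow-up, so this group could be large. The change over the longest exposure would then rest on those who stayed for all four sessions, with a wider interval than a model using all collected scores could give. The plan does not say how participants without session 4 are handled, and it leaves two definitions of change side by side.

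**Working it through.** **The plan's own precision figure.** The only design precision stated is a half-width of at most 11.9% for the exact 90% interval on the feasibility proportion (sections 18.3 and 21.2). It reproduces: with 27 of 54 the exact interval is 38.1% to 61.9%, half-width 11.89%. No precision figure is given for the BQ-II or PSEQ change.

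**Inputs.**
- From the documents: N = 54; four possible sessions; 60% follow-up target (0.60 × 54 = 32.4, so 33 at session 2); r = 0.73 for PSEQ from baseline to three months (8.24).
- Assumed: all 54 attend session 1; attendance at sessions 3 and 4, and alternatives at session 2; monotone drop-out; within-person correlation 0.6 to 0.73, either constant across sessions or decaying as r, r², r³; the same range for BQ-II, for which no correlation is given; covariance treated as known.

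**Formulas** (variances in units of the score variance).
- Paired: var = 2(1 − ρ₁₄)/n₄, where ρ₁₄ is the session 1 to session 4 correlation.
- Model with categorical session: var = c′I⁻¹c, with c = (−1, 0, 0, 1). I sums, over participants, the inverse covariance of the scores each one supplied.

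**Complete attendance, r = 0.73, constant.** Paired: 0.54/54 = 0.0100. Model: 0.0100. The ratio is 1.00, so the middle scores of four-session participants add nothing when everyone has four.

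**Attendance 54/33/22/16, r = 0.73, constant.**
- Paired: 0.54/16 = 0.03375.
- Sessions 1 and 4 only, but keeping all 54 baselines: (1 − r²)/16 + (1 − r)²/54 = 0.02919 + 0.00135 = 0.03054. SE ratio √(0.03054/0.03375) = 0.951.
- All available scores: 0.02729. SE ratio √(0.02729/0.03375) = 0.899.

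**Range for session 4 minus session 1** (SE ratio, model to paired, at r = 0.6 / 0.73):

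| Attendance, sessions 1/2/3/4 | Constant | Decaying | SE reduction |
|---|---|---|---|
| 54/33/22/16 | 0.89 / 0.90 | 0.81 / 0.82 | 10-19% |
| 54/33/27/22 | 0.91 / 0.93 | 0.85 / 0.86 | 7-15% |
| 54/33/31/30 | 0.95 / 0.96 | 0.90 / 0.92 | 4-10% |
| 54/45/40/35 | 0.95 / 0.95 | 0.91 / 0.92 | 5-9% |
| 54/50/48/46 | 0.98 / 0.98 | 0.97 / 0.97 | 1.8-3.5% |
| 54/54/54/54 | 1.00 / 1.00 | 1.00 / 1.00 | 0% |

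**Estimated unstructured covariance.** Simulation with 3,000 trials per setting, under the first two attendance patterns, gave SE ratios of 0.93-0.95 (constant) and 0.85-0.88 (decaying), a reduction of about 5-15%.

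**Session 2 minus session 1**, 33 pairs, r = 0.73. Paired: 0.54/33 = 0.01636. Model: 0.4671/33 + 0.0729/54 = 0.01551. SE ratio √(0.01551/0.01636) = 0.973, so this contrast gains only about 3%.

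**Scale.** With the cited BQ-II SD of 0.73, r = 0.73 constant and attendance 54/33/22/16, the SE of the one-to-four change is 0.134 paired (0.73 × √0.03375) and 0.121 by the model (0.73 × √0.02729).

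**The case against.** The strongest case against is that this is largely a preference of method. Aim 2 is exploratory, the study is a single-arm pilot, no test or precision target attaches to the change scores, and no feasibility decision depends on them. That stands, and it keeps the impact low.

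The size also rests on attendance that the documents do not give. With good retention the gain nearly vanishes. The top of the range further needs correlation decaying from 0.6-0.73 between adjacent sessions, which puts the session 1 to 4 correlation at 0.22-0.39 (0.6³ and 0.73³). That fits poorly with a cited 0.73 over three months. If the decay is set so that sessions 1 and 4 correlate at 0.73, the reduction is 11-16% for 16-22 completers. This stands too, so the figures must be read as a range.

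The narrower interval also belongs to a different quantity. The paired difference describes those who completed four sessions, while the model estimates change for all enrolled participants under missing at random. With few people at session 4 that assumption can hardly be checked. This has to be stated in the plan, but it does not defeat the proposal if both analyses are reported.

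A reader might infer more than the documents support:
- That scores from sessions 2 and 3 are merely plotted. They are not: both enter the per-time-point correlations, and session 2 normally enters the paired difference in 8.23 and 8.24.
- That using two of a four-session participant's four scores loses precision in itself. With complete data it does not, as the ratio of 1.00 shows.
- That the paired estimate is wrong. It is a valid description of completers, and nothing in the documents shows how those who leave early differ.

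**Conclusion.** The point holds in a limited form. The one-to-four change in 8.25.1 excludes all scores from participants who stop before session 4, session 3 has no planned change estimate, and no model is specified that would use these data. The SE of that change would fall by about 7-19% if 16-22 of 54 reach session 4, about 4-10% if 30-35 do, about 2-4% if 46 do, and 0% if all do. These figures assume known covariance, correlation 0.6-0.73 (the upper value cited for PSEQ only) and missing at random; an unstructured covariance gains less. This is a cheap improvement to an exploratory aim. It is not a flaw in the feasibility endpoint or in the sample size.

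**What to change.** In sections 8.23 to 8.25.1, specify one linear mixed model per scale, fitted to all available scores, with session 1-4 as a categorical factor and within-person correlation modelled. Name the covariance structure in advance. Report the session 2 minus 1 and session 4 minus 1 contrasts with 90% confidence intervals. Naming both also reconciles the two definitions of change. Keep the simple paired differences as a supporting analysis in those who attended, and keep the planned plots and correlations. State that the model targets change in all enrolled participants, that the paired analysis describes attenders, and that the model relies on missing at random.

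The cost is a short change to the analysis text and a little statistician time. It needs no new data and adds no burden for participants. The downside is the covariance assumption and the missing-at-random assumption; reporting the paired results alongside lets readers see how far the two analyses differ.

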9.0 Procedures Involved*

Testing Feasibility of Motivational Interviewing for Patient-Reported Cancer Pain Goals

9.1 Study design:

This is a single-arm pilot study to assess feasibility and acceptability of a motivational interviewing intervention which will entail two-to-four intervention sessions per participant, participant completion of a battery of questionnaires specific to the intervention session, an investigator-led MI intervention at each session, and summary statistics (described below).

9.2 Study Procedures:

After written informed consent has been obtained and verbal consent confirmed participation in this study will involve between two and four intervention sessions.

9.21 Study Participation Compensation: Participants will be compensated with \$25 gift cards at the first and last visits (anticipated to be visits 1 and 4). Pending receipt of additional funding for participant compensation, participants may also be compensated at visits 2 and 3, if these are in addition to the first and last visits, and if this funding is granted to the research study.

9.22 Intervention Sessions: Each intervention session will include a battery of questionnaires, an MI intervention, and the investigator completing a goal(s) summary for the participant to take away. Participants may opt to complete Intervention Sessions 2, 3, and 4 in person on the DFCI campus or via telephone (or a mix). Session-specific content is outlined below. Session-specific content outlined below.

Testing Feasibility of Motivational Interviewing for Patient-Reported Cancer Pain Goals

Session 1:

Questionnaires:	Demographics survey* Pain location diagram (paper and pencil) BQ-II* PSEQ*
MI Intervention	Investigator-led discussion (described below)
Goals Summary	Completed by investigator
Gift Card (\$25)	Disbursed

* Paper and pencil form or tablet computer per participant preference.

Sessions 2 & 3:

Questionnaires:	BQ-II* PSEQ*
MI Intervention	Investigator-led discussion (described below)
Goals Summary	Completed by investigator
Gift Card (\$25)	None (Pending additional funding)

* Paper and pencil form or tablet computer per participant preference.

Session 4:

Questionnaires:	BQ-II* PSEQ* PEQ*
MI Intervention	Investigator-led discussion (described below)
Goals Summary	Completed by investigator
Gift Card (\$25)	Disbursed

* Paper and pencil form or tablet computer per participant preference.

Testing Feasibility of Motivational Interviewing for Patient-Reported Cancer Pain Goals

Motivational Interviewing Sessions:

Motivational Interviewing Intervention:
 
An investigator-led discussion about the participant's pain experience which is focused on the participant reporting of functional pain goals (FPGs). The investigator will elicit questions and goals that participants will be encouraged to discuss with their palliative care providers.
	
Key elements of intervention:
 
• Establish rapport• Open and closed questions• Reflecting• Gaging ambivalence• Permission to give information• Pain-related problems• Feelings related to pain meaning• Perceptions about what will happen with the pain• Desired pain management outcomes (FPGs)• Pain management interventions acceptable to participant
-----------------------------------------------------------------------------------------------------------------------------------------------------------------------------------------------------------------------------------------------------------------------------------------------------------------------------------------------------------	----------------------------------------------------------------------------------------------------------------------------------------------------------------------------------------------------------------------------------------------------------------------------------------------------------------------------------------------------------------------------------------------------------------------------------------------------------------------------------------------------------

9.3 Data to be collected:

Source data will be collected in the battery of questionnaires described above. All source data questionnaires are included at the end of this protocol. These source data documents and records, except for the IRB-approved written informed consent document will be labeled with numeric identifiers only to protect participants confidentiality. All paper versions will be filed in a secure locked filing cabinet in the PI's office at the Cantor Center, accessible to research study team members. All digital data source records will be retained in REDCap (demographics, BQ-II, PSEQ, PEQ) or in study spreadsheets in the Cantor Center shared drive protected by Partners IS, or on the encrypted laptop computer of the PI.

9.4 Participant Registration:

Institutions will register eligible participants in the Clinical Trials Management System (CTMS) OnCore as required by DF/HCC SOP REGIST-101.

10.0 Data Banking*

10.1 Questionnaires

Survey data from the questionnaires, including demographics, BQ-II, PSEQ, and OET, and MI intervention session audio-recordings will be stored in the Cantor Center shared drive protected by Partners IS, or on the encrypted laptop computer of the PI for the IRB-required time frame.

Testing Feasibility of Motivational Interviewing for Patient-Reported Cancer Pain Goals

10.2 Transcripts

De-identified transcripts from the MI intervention sessions will be banked by the Cantor Center for future research purposes such as qualitative data analysis. These files will be stored securely in the Cantor Center shared drive protected by Partners IS.

10.3 Accessing

Researchers, including investigators from collaborating institutions, can request de-identified data from this study for new research. Data may also be shared with outside non-profit academic investigators. Researchers may request access by making a request in writing to the PI and submitting appropriate IRB approval processes.

11.0 Data Management* and Confidentiality

11.1 Analysis:

Statistical data analysis will be conducted by the research team statistician. Testing procedures were outlined in section 8.2, above.

MI intervention fidelity testing will be conducted on 33% of the audio-recorded sessions, by the PI or RA, as described above. The number of sessions to be reviewed assuming a total sample of 54 participants, seen for two interventions at least ($108 \times .33$) will be 37, and will be conducted on a bi-weekly schedule.

11.2 Training:

The study will be reviewed and approved by the Dana Farber Cancer Institute IRB. The PI and study staff will have completed the Collaborative Institutional Training Initiative Human Subjects Training Program and all other training required by DFCI. In addition, the PI and study staff will also practice the informed consent process with the RA(s). Before beginning the research study, the PI will obtain written and dated approval from the IRB for the study protocol, written informed consent form, EMR abstraction forms, subject recruitment procedures, and any written information to be provided to subjects. Any future protocol amendments or consent form updates must also be approved by the IRB.

The PI will provide education to the research team members about participant eligibility identification, recruitment, and consenting training, participant entry into the study data spreadsheet, and use of the MISCHE for fidelity evaluation.

12.0 Withdrawal of Subjects*

12.1 Participant withdrawal:

Unless the patient's clinician states that the study is no longer in their best interest, there are no anticipated circumstances in which a patient will be withdrawn from the research without their consent. If a patient requests to be removed from the research study, we will document their reason for dropping out of the study and update their status in OnCore.

13.0 Potential Risks to Subjects*

There are no physical risks to taking part in this research. The risks related to this study include a risk for loss of privacy and also the risk that some items on the questionnaires might cause feelings of unease or distress. If talking about their cancer pain experience is upsetting, the researcher will arrange a visit with a medical social worker, or provider in the clinic. There is a possibility that participants could experience physical pain from their cancer during the interventions sessions. The PI is a board-certified hospice and palliative care nurse with

Testing Feasibility of Motivational Interviewing for Patient-Reported Cancer Pain Goals
experience assessing and providing nursing interventions for discomforting symptoms. She will intermittently ask participants if they are experiencing discomforting pain. If so, they will be prompted to follow their medication orders and asked if they would like to reschedule the intervention appointment. The nature of risks to subjects is low, and the anticipated risks are likely to be reversible within minutes-to-hours.

